10.0 Statistical Considerations

Baseline variables known to be associated with parenting including age, sex, income, and marital status will be compared by treatment group using the Kruskal-Wallis test (continuous variables) or Pearson's Chi-squared test (categorical variables). We will also examine if diabetes-related variables (e.g., duration of diabetes, baseline A1C) are associated with treatment group. *A priori*, we assume that our block randomization will lead to well-balanced groups so that we will not need to control for additional confounders.

Effects of the Intervention: We will estimate the effect of the intervention on each of the continuous outcomes by fitting linear mixed-effects models developed. In modeling, outcomes will be considered at their key time-points (baseline, 3 months, 6 months, and 12 months) with treatment group and the interaction of treatment with time serving as the main explanatory variables. Such a model will allow us to test for any differences between treatment and control groups over time while accounting for baseline values. While the randomized block design should minimize confounding, we will adjust for age, income, and marital status to improve precision. The results from the adjusted and unadjusted models will be compared with respect to their estimates of the treatment effects. Our interpretation will focus on describing clinically relevant treatment effects (e.g., A1C reductions of $\geq 0.5\%$, >1 additional glucose check per day, reduction from moderate to mild depressive symptoms) with corresponding confidence intervals, rather than just significance testing. We will include a random intercept to account for within-subject correlation. The error structure of the model is assumed to be compound symmetric, and the validity of this assumption will be examined by computing Akaike Information Criteria against other common structures. Subjects will be included in the analysis if they have an outcome measured at baseline and at least one outcome measured 6 or 12 months later.

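### Entered as main effects, age, income and marital status add almost no precision to a treatment-by-time effect; the plan should name the contrast and say how the covariates enter

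*Combined protocol and SAP*

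**What the plan says.** All of this is in section 10.0, under Effects of the Intervention.

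- Baseline is one of the four modelled outcome visits, alongside 3, 6 and 12 months.
- The model has "treatment group and the interaction of treatment with time serving as the main explanatory variables". The plan says that this tests group differences over time and takes baseline values into account.
- On correlation: "We will include a random intercept to account for within-subject correlation", and "The error structure of the model is assumed to be compound symmetric", to be checked by AIC against other structures.
- On covariates: "we will adjust for age, income, and marital status to improve precision". No covariate-by-time term is named.
- On the check: "The results from the adjusted and unadjusted models will be compared with respect to their estimates of the treatment effects".
- On the analysis set: "Subjects will be included in the analysis if they have an outcome measured at baseline and at least one outcome measured 6 or 12 months". Incomplete follow-up is therefore admitted, and the power paragraph expects 2 to 4 measurements per subject.

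The plan does not say which coefficient or contrast is the treatment effect.

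**The concern.** When baseline sits on the outcome side with its own group difference, the term that takes baseline into account is treatment-by-time, a contrast of within-dyad changes. Age, income and marital status at enrolment are constant within a dyad. As main effects they add the same amount at every visit and so subtract out of any change. What they sharpen is the treatment main effect, which in this model is the group difference at baseline.

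Two stated purposes are at stake. The gain in precision would hardly occur. The comparison of adjusted with unadjusted effects would agree almost by construction, and a reader could take that agreement as evidence of robustness.

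**Working it through.** **Inputs.** From the power paragraph of section 10.0: A1C SD 1.16, correlation 0.60, difference 0.5, 80% power, alpha 0.05, 130 analysed, and SCI SD 4.2 with correlation 0.82. From section 5.0: equal allocation. Two-sided testing is assumed.

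**1. The plan's own sample sizes.** For a difference between arms in a quantity with variance V, N = 4 × (1.960 + 0.842)² × V / 0.5², with (1.960 + 0.842)² ≈ 7.849 and SD² = 1.3456.

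- Mean of 4 visits: V = 1.3456 × (1 + 3 × 0.60)/4 = 0.942. N = 118.3, or 120 after rounding up per arm; 122 with the t distribution. The plan states 122.
- Mean of 2 visits: V = 1.3456 × (1 + 0.60)/2 = 1.0765. N = 135.2, or 136; 138 with t. The plan states 138.
- Mean of three follow-ups minus baseline: V = 1.3456 × (2.2/3 + 1 − 1.2) = 0.718. N = 90.1, or 92; 94 with t. This does not give 122.
- Single-visit change: V = 1.3456 × 2 × (1 − 0.60) = 1.0765, the same as the mean of 2 visits. The 138 therefore cannot separate the two readings.
- SCI, N = 130: the detectable difference for a mean of two visits is 2.802 × √(4 × 4.2² × 0.91/130) = 1.97, matching the stated 2.0. For a change it would be 2.802 × √(4 × 4.2² × 0.36/130) = 1.24.

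The stated figures reproduce, and they match a time-averaged group difference.

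**2. Cancellation with complete visits.** For dyad i at visit j, with arm G and covariates W, and δ = 0 at baseline:

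Y_ij = μ_j + αG_i + δ_jG_i + γW_i + b_i + e_ij

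Y_ij − Y_i0 = (μ_j − μ_0) + δ_jG_i + (e_ij − e_i0)

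γW_i has gone. Under compound symmetry the data split into dyad means and within-dyad deviations. The δ_j come from the deviations, and the covariates enter only the means. Estimate and SE are therefore unchanged: at N = 130, the SE of the 12-month contrast is √(1.0765 × 4/130) = 0.182 either way. Under another covariance structure the estimate still cancels for a given covariance matrix, though re-estimating that matrix could move the SE slightly.

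**3. Incomplete visits.** REML random-intercept fits to simulated trials: N = 130, SD 1.16, correlation 0.60, 150 data sets per setting, with the plan's inclusion rule applied. Assumptions not in the documents: the covariates explain 10%, 20% or 40% of total A1C variance, and follow-up visits are missing at random. Entries are the SE ratio (adjusted/unadjusted) for 12-month treatment-by-time and, in brackets, the SD of the difference between the two estimates in A1C points.

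| R² | 0% missing | 10% | 20% | 30% |
|---|---|---|---|---|
| 0.1 | 1.0000 (0) | 0.9998 (0.005) | 0.9995 (0.007) | 0.9992 (0.009) |
| 0.2 | 1.0000 (0) | 0.9994 (0.007) | 0.9985 (0.010) | 0.9979 (0.015) |
| 0.4 | 1.0000 (0) | 0.9980 (0.011) | 0.9961 (0.018) | 0.9930 (0.024) |

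The largest difference in any one data set was 0.094, at R² 0.4 with 30% missing.

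**4. Where main-effect adjustment does help** (same simulations, complete visits, R² 0.1, 0.2, 0.4).

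- Time-averaged treatment coefficient: SE ratio 0.94, 0.85, 0.67.
- Treatment-by-time with baseline means constrained equal: 0.99, 0.97, 0.92. The constraint by itself lowers the SE by about 11% (ratio 0.89).

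**5. Covariate-by-visit terms.** Here R² is the share of the variance of *change* that the covariates explain. With p covariate terms, the SE ratio is about √[(1 − R²)(1 + p/(N − p − 3))]. With N = 130 and p = 3 or 4:

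- R² = 0: √(1 + 3/124) = 1.012 and √(1 + 4/123) = 1.016, a rise of 1.2-1.6%. Simulated mixed models agreed (1.009 to 1.016).
- R² = 5%: × √0.95 gives 0.986 and 0.990, a fall of 1.0-1.4%.
- R² = 15%: × √0.85 gives 0.933 and 0.937, a fall of 6.3-6.7%.

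**The case against.** The strongest reply is that the cancellation belongs to a reading and not to the text. The plan says only that it will adjust. It lists treatment group as well as the interaction as explanatory variables and never names the effect. Its 122 for A1C and 2.0 units for SCI match a time-averaged difference, for which main-effect adjustment cuts the SE by 6-33% under the assumed R². This stands, and it is why the point is conditional. It does not settle the matter in the plan's favour: an average that includes the pre-treatment visit dilutes the effect and does not take baseline into account, as the plan says its model does. Where the plan wants interactions (treatment-by-time, and moderators under the Exploratory Aim), it says so.

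A reader might infer more than the documents support in three ways.

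- *The two models must give the same answer.* That needs complete visits, and the plan expects 2 to 4 per subject. Section 7.0 also lets participants skip questions, so dyads without income data could drop out of the adjusted fit and move its estimate.
- *Chance imbalance in, say, age biases the result.* Under randomization it is random error already inside the confidence interval. If A1C change differed by 0.3 points per SD of age (an assumption), the imbalance would have SD 0.3 × 2/√130 = 0.053 against an SE of 0.182, or (0.053/0.182)² ≈ 8% of the variance. That is the precision question again, not a second harm.
- *Covariate-by-visit terms are sure to gain precision.* The documents do not say how well these covariates predict change; they describe them as related to parenting. With no prediction, the terms cost 1-2%.

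**Conclusion.** The concern holds conditionally. If the effect is treatment-by-time with a free baseline difference and the covariates are main effects, adjustment changes nothing with complete visits and almost nothing with incomplete ones. The SE gain is at most about 0.7%, and the estimates usually lie within about 0.02 A1C points of each other. These limits rest on assumed covariate R² of 0.1-0.4 and on 10-30% of follow-up visits missing at random. On that reading the stated gain in precision is not delivered, and the planned model comparison says almost nothing about robustness.

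The unadjusted estimate is valid, no bias is shown, and the stated sample sizes of 122 and 138 are unaffected. This is a recommended change of wording that makes a planned adjustment do its job.

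**What to change.** Name the treatment contrast and say how the covariates enter. Suggested wording: *The treatment effect is the treatment-by-visit contrast at 6 and 12 months relative to baseline. The adjusted model includes age, income and marital status and the interaction of each with visit.* Apply it to all continuous outcomes. The comparison with the unadjusted model then becomes informative.

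An alternative is to constrain the baseline means to be equal across arms, as randomization justifies, and keep the covariates as main effects.

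Under either option, say how missing income will be handled, so that both models use the same dyads.

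The cost is one or two sentences and no new data. The interactions use 9 to 12 degrees of freedom (3 or 4 covariate terms × 3 follow-up visits) and raise the SE by 1-2% at worst. The constraint uses none.

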Examining mediators will provide evidence for the mechanisms of change, offering direction for program implementation and future research. Investigating mediators of the intervention also allows us to test the theoretical basis and the effect of intervention on separate outcomes,¹⁰⁷ such as glycemic control, and psychosocial outcomes. To assess direct and indirect effects of potential mediator variables, we will follow the steps outlined by MacKinnon and colleagues^{108,109} to establish mediation. The bootstrap method will be used to obtain a 95% confidence interval for the total, direct, and indirect effects. We will test maternal depressive symptoms and parental involvement as mediators of treatment effects, maintaining consistent temporal ordering, by considering baseline randomized treatment, 3-month depressive symptoms and parental involvement variables as the mediators, and 6-month outcomes (treatment effects), as well as 12-month outcomes (sustained treatment effects). Our longitudinal data will also allow us to consider additional analyses that account for the bidirectional relationships between family functioning and depressive symptoms.

To determine the feasibility of the intervention, we will examine recruitment and retention data. In addition, fidelity checks will be conducted by reviewing 20% of the telephone sessions, which will be coded for content by an independent rater. We propose a feasibility benchmark of $\geq 90\%$ fidelity. To evaluate acceptability of the intervention, we will examine participation (phone call attendance), adherence (completion of homework), and satisfaction ratings. We propose a feasibility benchmark of $\geq 80\%$ attendance. We will also conduct exit interviews with mothers, which will be analyzed with a content analysis approach to identify themes across participants.

[figure not shown]
Assessing biases caused by dropouts: Some subjects may not return for their follow-up visit and hence have missing values of their response variables. Frequently, such subjects ("dropouts") are not a random sample of the entire cohort and an analysis of only the complete cases will bias the results. Indirect information about the nonrandom dropouts will be obtained by using binary logistic regression to predict dropout status on the basis of all baseline predictor variables.

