Exploratory Aim: Examine the differential impact of intervention effects across demographic factors (i.e., marital status, income, adolescent age, and sex).

While evaluating the main effects of interventions is critical to improving health outcomes, it is equally important to examine moderators of randomized clinical trials – even those that are unsuccessful – in order to determine *for whom* interventions may work. Based on findings from the literature and our own earlier work, we will examine potential moderators, with a focus on marital status, income, and adolescent age and sex. Moderators will be tested by including an interaction term with treatment group in the regression models.

Power and sample size:

We plan to enroll 154 subjects so that, after allowing for a 15% attrition rate, 130 subjects will be available for analysis. Preliminary data from our pilot study with 30 adolescents indicates that mean A1C is 9.0% with a standard deviation of 1.16% and a correlation between repeated measurements over time of 0.60. Under these assumptions, we will have 80% power to detect a 0.5% difference in A1C if 122 subjects are measured at all 4 time points or if 138 subjects are measured only twice (out of 4 possible time points). Since we expect to obtain ≥ 3 measurements on most of subjects, enrolling 130 subjects with 2 to 4 measurements each will provide sufficient power for Aim 1. For the SCI (a measure of adherence), using preliminary data in 30 subjects we estimated baseline scores of 23.6 ± 4.2 with a correlation among repeated measures over time of 0.82. With 130 subjects measured at least twice, we will have 80% power to detect a 2.0 unit change due to treatment, which is an 8.5% difference from baseline.

Power calculations for mediation models were considered assuming 130 subjects will be available for analysis. In preliminary data, partial correlations of the mediators, PHQ9 and DFC, with A1C were 0.20 and 0.51, respectively. Correlations of the mediators with treatment were 0.52 and 0.54, respectively. Under these assumptions, we have 63% power to detect an indirect effect of treatment on A1C through PHQ9 and >99% power to detect an indirect effect of treatment on A1C through DFC. Calculations assume a 0.05 significance level.

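### The analysis-set rule drops randomised dyads whose only follow-up is month 3, a post-randomisation exclusion that the planned four-visit mixed model does not need

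*Combined protocol and SAP*

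**What the plan says.** All statements below are in section 10.0 unless another section is named.

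- **Model.** Under Effects of the Intervention, "outcomes will be considered at their key time-points (baseline, 3 months, 6 months, and 12 months"), with treatment and treatment-by-time as the main terms. On correlation: "We will include a random intercept to account for within-subject correlation", with compound symmetry assumed and checked against other structures.
- **Analysis set.** The same paragraph ends with the inclusion rule, under which a dyad's data are "included in the analysis if they have an outcome measured at baseline and at least one outcome measured 6 or 12 months later".
- **Dropouts.** The plan says such subjects frequently "are not a random sample of the entire cohort and an analysis of only the complete cases will bias the results". The only step it then describes is "binary logistic regression to predict dropout status on the basis of all baseline predictor variables".
- **Timing of effects.** The mediation text takes the mediators at month 3 and the outcomes as "6-month outcomes (treatment effects), as well as 12-month outcomes (sustained treatment effects").
- **Sample size.** "We plan to enroll 154 subjects so that, after allowing for a 15% attrition rate, 130 subjects will be available for analysis". The power text counts subjects with any two to four of the four measurements. It does not require one of them to be at month 6 or 12.

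Month 3 is a scheduled visit for mother and adolescent (section 6.0), and randomisation follows baseline collection (section 5.0). No intention-to-treat set, imputation or missing-data sensitivity analysis is stated.

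**The concern.** Whether a dyad has a 6- or 12-month value is settled after randomisation, so the rule conditions the treatment comparison on a post-randomisation event. A dyad with baseline and month 3 fails the rule, although a likelihood-based mixed model takes incomplete outcome vectors. Its month-3 value informs the month-3 contrast directly and the later contrasts through the within-subject correlation.

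Two things are at stake. Data already collected are thrown away, which costs precision. Also, if leaving after month 3 depends on the response seen by then, those who remain are a selected group, and the contrast between arms can be biased. The dropout regression uses baseline predictors only; it describes dropout and returns no dyad to the analysis.

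**Working it through.** **Inputs from section 10.0.** A1C SD 1.16 and correlation 0.60; SCI SD 4.2 and correlation 0.82; target A1C difference 0.5; 154 enrolled and 130 analysed, so 65 per arm at the 1:1 allocation of section 5.0.

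**Inputs assumed.** The number m of month-3-only dyads per arm and the dropout mechanism. The largest case, m = 12, comes from 154 − 130 = 24. It puts the whole planned attrition into this group, and that attrition is an allowance, not an upper bound.

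**1. The plan's own figures.** The variance of a mean of k measures is 1.16² × (1 + 0.60(k − 1))/k, which is 1.3456 × 0.70 = 0.942 for k = 4 and 1.3456 × 0.80 = 1.076 for k = 2. Total N = 4 × (1.960 + 0.842)² × variance / 0.5² gives 118.3 and 135.2, or 120 and 136 after rounding up each arm. The plan states 122 and 138, and 154 × 0.85 = 130.9 against its 130. The inputs are therefore being used as the plan used them.

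**2. Precision.** Take 65 dyads per arm with four visits, with or without m more that have baseline and month 3 only, under compound symmetry.

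- Variance of a change from baseline: 2σ²(1 − ρ) = 2 × 1.3456 × 0.40 = 1.0765.
- Part not predictable from baseline and month 3: σ²(1 − 2ρ²/(1 + ρ)) = 1.3456 × 0.55 = 0.7401. The predictable part is 1.0765 − 0.7401 = 0.3364.
- SE at month 3 = √[2 × 1.0765/(65 + m)].
- SE at month 12 (month 6 is the same) = √[2 × (0.7401/65 + 0.3364/(65 + m))].

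| A1C contrast | Rule (m = 0) | m = 3 | m = 6 | m = 12 |
|---|---|---|---|---|
| Month 12 | 0.182 | 0.181 | 0.180 | 0.178 |
| Month 3 | 0.182 | 0.178 | 0.174 | 0.167 |

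For the SCI at month 12 with m = 12, the same formulas give 0.442 under the rule and 0.432 with all data.

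**3. Bias when leaving depends on the change already seen.** The 0-to-3-month change has SD √1.0765 = 1.04, with mean 0 in control and −0.5 in the intervention arm. Dropout after month 3 is logistic in that change. The intercept is set to give the stated rate: averaged over arms when the mechanism is shared, within the affected arm when it is not. The month-3 bias is the shift in the difference between arms among those who stay, found by numerical integration. Under compound symmetry the 12-month change regresses on the 3-month change with slope σ²(1 − ρ)/[2σ²(1 − ρ)] = 0.5, so the 12-month bias is half the month-3 bias. Absolute values at 12 months:

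| Log-odds per 1% A1C | 15%, shared | 15%, one arm | 7.5%, shared | 7.5%, one arm |
|---|---|---|---|---|
| 1 | 0.024 | 0.071 | 0.015 | 0.037 |
| 0.5 | 0.008 | 0.039 | 0.004 | 0.020 |
| 0.25 | 0.002 | 0.020 | 0.001 | 0.010 |

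Random dropout gives zero. If it is the worsening dyads that leave, a shared mechanism pulls towards no effect, an intervention-only mechanism overstates the effect and a control-only mechanism understates it. In a simulation of the one-arm case at 15% dropout with 1,000,000 dyads per arm, the all-data fit came within 0.003 of the truth.

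**4. Bias when leaving depends on the month-3 level.** The covariance of the month-3 value with the baseline-to-12-month change is σ²(ρ − ρ) = 0, so with an unconstrained baseline there is no bias at months 6 and 12. At month 3 (15%, one arm, log-odds 1), the mean month-3 value of those who stay shifts by 0.172 and their baseline by 0.60 × 0.172 = 0.103, leaving a bias of about 0.07. Simulations with about 12% dropout, related to the level in control only (log-odds 1 per SD), give about −0.47 at months 6 and 12 for a true −0.50 if baseline means are constrained equal. With an unconstrained baseline and an assumed decaying correlation (0.85 per three months), they give about −0.53 at month 12.

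**5. Bias when leaving depends on the unseen 12-month change** (15%, intervention arm only). The 12-month bias is 0.08 under the rule and 0.06 with all data at log-odds 0.5, and 0.14 and 0.10 at log-odds 1. Using all data reduces this bias but does not remove it.

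**The case against.** The strongest reply is that little turns on this. The plan names 6- and 12-month outcomes as the treatment effects, and month 3 mainly supplies mediators. At 12 months the standard error moves from 0.182 to 0.178 only if all 24 planned losses fall between months 3 and 6. Dyads that also miss month 3 gain almost nothing from the change, and those that leave after month 6 are already kept. The largest bias in the table is 0.071/0.182 = 0.39 standard errors, and it needs dropout related to response in one arm only. Nothing in the documents points to that: both arms receive seven calls and daily posts. Dropout on the month-3 level gives no 6- or 12-month bias under the stated model.

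Two further points are fair. The plan's warning concerns analyses of complete cases only, whereas this rule keeps anyone with a 6- or 12-month value, so the warning applies in part. Also, admitting dyads with any measurement brings in baseline-only dyads, which add almost no information.

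What stands is the limit on size. None of this shows that the exclusion is needed. Interest in months 6 and 12 justifies choosing those contrasts, not requiring a 6- or 12-month value from every dyad. Month 3 is itself a modelled time point, and there the loss is plainer. Baseline-only dyads do no harm in a likelihood-based model.

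**Conclusion.** The concern holds and should be fixed. The rule is in force, it excludes dyads with baseline and month 3 only, and nothing elsewhere in the plan restores them. That the exclusion is avoidable is certain; how much it matters is not.

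The exposure is greatest at month 3. At 12 months the expected effect is small unless dropout depends strongly on response in one arm only. The precision figures assume compound symmetry and 65 fully observed dyads per arm; the bias figures also depend on the assumed mechanism. Using all available data removes the selection bias only if missingness depends on observed data and the covariance model is adequate; otherwise it reduces it, as in step 5. The planned sample size is not called into question.

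**What to change.** Replace the inclusion sentence at the end of the Effects of the Intervention paragraph with:

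> All randomised dyads with at least one outcome measurement at any visit (baseline, 3, 6 or 12 months) are included in the mixed model in their assigned group.

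Keep the present set (baseline plus a 6- or 12-month value) as a sensitivity analysis. The logistic regression of dropout can stay as a description of who leaves.

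The cost is one sentence of analysis-plan wording, with no new data and no change to the model. It also brings the analysis set into line with the power text, which already counts subjects measured at any two of the four time points.

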At baseline and 6 months data collection, adolescent-mother dyads will participate in a 15-minute videotaped conversation about diabetes-related stress. To choose the topic for the video interaction, we will use the mother's highest-rated stressor on the Response to Stress Questionnaire (Connor-Smith, Compas, Wadsworth, Thomsen, & Saltzman, 2000), completed as part of the survey data collection, which lists diabetes-specific stressors. Mothers will rate the frequency of each stressor (e.g., worrying about "bad" numbers, remembering diabetes supplies) on a 4-point Likert scale ranging from 0 (never) to 3 (almost every day). Each dyad will be given a cue card with questions regarding the highest-rated stressor (e.g., What happened the last time we [had to] you remember diabetes supplies], what kind of emotions do we have when we [have to remember diabetes supplies]? How can we reduce this stress?) to guide their discussion during the videotaped interaction. This protocol has been used successfully in other studies conducted by [name], and she has trained several cohorts of raters on the Iowa Family Interaction Rating Scales to be reliable coders.

The interaction will be recorded using study iPads. Video files will be transferred from the passcoded iPad to an encrypted study computer, and then uploaded to Enterprise Storage, the secure, shared drive. Video files will only be viewed by KSP.

Mothers in the study will have 7 individual phone calls with a trained member of our research staff to discuss the information in the binders. Calls will last approximately 10-30 minutes. Mothers assigned to the Communication & Coping group will discuss content related to coping with diabetes-related stress and positive parenting strategies, following the study manual mailed to participants after randomization. The content of this manual was reviewed by a coder trained in health literacy at Vanderbilt's Effective Health Communication Core. Each session was given a Suitability Assessment of Materials (SAM) score to objectively assess the materials for clear communication and health information design (content, literacy demand, graphics, layout and typography, learning stimulation, and cultural appropriateness). Scores of 70% to 100% are considered superior material suitable for low health literacy individuals (Doak, Doak, & Root, 1996). On the SAM scale, our sessions were rated 78% to 86%, with a reading

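### The A1C mediation models name no adjustment for baseline mediator, baseline A1C or 3-month A1C, so if A1C affects the mother the indirect-effect test is positive far more often than 5% when the mediator does nothing

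*Combined protocol and SAP*

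**What the plan says.** Aim 1 (Section 2.0) asks whether effects on adolescents' diabetes outcomes come about through maternal depressive symptoms and parental involvement. Section 10.0 sets the time order "by considering baseline randomized treatment, 3-month depressive symptoms and parental involvement variables as the mediators, and 6-month outcomes (treatment effects"), and adds 12-month outcomes as sustained effects. The inference is an interval: "The bootstrap method will be used to obtain a 95% confidence interval for the total, direct, and indirect effects". The steps come from cited sources, and no covariates are listed for the mediation models.

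Three other statements bear on this:

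- Section 10.0 assumes that randomization makes control for further confounders unnecessary. It names age, income and marital status only for the mixed models.
- The further longitudinal analyses are optional and concern "bidirectional relationships between family functioning and depressive symptoms". A1C is not part of them.
- The power text says "partial correlations of the mediators, PHQ9 and DFC, with A1C were 0.20 and 0.51, respectively". It gives no timing, direction or conditioning variables for these figures.

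A1C is an outcome at baseline, 3, 6 and 12 months, and Section 6.0 aligns the questionnaires with clinic visits. A 3-month A1C is therefore planned alongside the 3-month mediator.

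**The concern.** Randomization protects the comparison of arms on the mediator and on A1C. It does not protect the association between mediator and A1C within arms. The plan relies on the three-month lag for that, but the lag helps only if A1C at the mediator visit is taken into account. A mother whose child has high A1C at 3 months may report more symptoms then, and the child's A1C will tend to be high at 6 months whatever she feels. The protocol itself treats the illness as a stressor for mothers, and one of its example stressors in Section 6.0 is "worrying about 'bad' numbers".

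If the intervention lowers maternal symptoms and the mediator-A1C association is of this reverse kind, the product of the two paths is non-zero although the mediator does nothing to A1C. The stake is the mechanism claim in Aim 1, which is meant to guide implementation. The treatment-effect estimates from the mixed models are not affected.

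**Working it through.** **Inputs from the documents.** Section 10.0, power text: N = 130 ("Power calculations for mediation models were considered assuming 130 subjects will be available for analysis"); A1C SD 1.16%; correlation between repeated A1C values 0.60; partial correlation of mediator with A1C 0.20 (PHQ-9) and 0.51 (conflict, DFC); correlation of treatment with mediator 0.52 and 0.54; stated power 63% and >99%; "Calculations assume a 0.05 significance level", taken here as two-sided. Section 5.0: equal allocation.

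**Assumed, not in the documents.** The correlation c between the 3-month mediator and 3-month A1C, given treatment, and its direction (A1C to mother). The pilot values are used for c, with a range.

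**Step 1. The plan's own power.** Power for a correlation r with k conditioning variables is Φ(atanh(r)·√(N − 3 − k) − 1.96).
- Treatment to PHQ-9: 0.576 × √127 = 6.49, power above 99.99%.
- PHQ-9 to A1C: 0.2027 × 11.27 = 2.285; 2.285 − 1.96 = 0.325; Φ = 62.7%.
- The product is 62.7%, against 63% stated. Both DFC paths exceed 99.99%, against >99% stated.

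**Step 2. False-positive rate as planned.** Let the mediator have no effect on A1C and let 3-month A1C drive it. The induced correlation with 6-month A1C is 0.60 × c: 0.60 × 0.20 = 0.12 for PHQ-9 and 0.60 × 0.51 = 0.306 for DFC. With treatment in the model, √126 = 11.22.
- PHQ-9: 0.1206 × 11.22 = 1.353; Φ(1.353 − 1.96) = 27%.
- DFC: 0.316 × 11.22 = 3.55; Φ(3.55 − 1.96) = 94%.

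The treatment-mediator path is almost always significant, so these are the rates at which an indirect effect is found. Simulation with N = 130 agrees: 28% and 94% by joint significance (3,000 trials), and 29% and 95% by percentile bootstrap (800 and 300 trials).

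| Assumed c | Indirect effect found (nominal 5%) |
|---|---|
| 0.10 | about 12% |
| 0.20 | about 28% |
| 0.30 | 51–57% |
| 0.40 | 79% |
| 0.51 | 94–95% |

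A 0.5-point treatment effect on 3- and 6-month A1C leaves these rates essentially unchanged.

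**Step 3. Size of the spurious effect.** With equal arms, the treatment difference in the mediator is 2r/√(1 − r²) within-arm SDs, and the indirect effect is that × 0.60c × 1.16.
- PHQ-9: 1.218 × 0.12 × 1.16 = 0.17 A1C points.
- DFC: 1.283 × 0.306 × 1.16 = 0.46 points.

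Both point towards benefit. The design difference is 0.5.

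**Step 4. What adjustment does.** Given baseline A1C, the mediator's correlation with 6-month A1C is (0.60c − 0.36c)/√((1 − 0.36c²)(1 − 0.36)).
- PHQ-9: 0.048/0.794 = 0.060, a rate of about 10%.
- DFC: 0.1224/0.762 = 0.161, a rate of about 44%.

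Simulation with baseline mediator and baseline A1C gives 11% and 47%. Given 3-month A1C the correlation is zero; simulation of the full model gives 7% and 6%.

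**Step 5. A different driver.** If the adolescent's stable A1C level drives the mediator, c applies at every visit and the planned test sees c itself. The rates are then 62% and 100%, essentially the stated power. Given baseline and 3-month A1C, the remaining correlation is 0.25c/√((1 − 1.25c²) × 0.55).
- PHQ-9: 0.05/0.723 = 0.069, a rate of 11–12%.
- DFC: 0.1275/0.609 = 0.209, a rate of about 66%.

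Adding the baseline mediator leaves about 11% and 53% in simulation.

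**Step 6. Price of the 3-month adjustment.** Under true mediation, simulated power for PHQ-9 is 63–66% as planned. With 3-month A1C added it is 70% if none of the effect has reached A1C by month 3, 53% if half has, and 34% if all has. For DFC it stays at 97% or more.

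**The case against.** **The plan is silent; it does not exclude the adjustment.** The cited steps may include covariates. That is true, and the supportable statement is that none is specified. Silence still leaves the choice to be made after the data are seen.

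**A null treatment effect would show.** The plan reports total and direct effects as well. If treatment did nothing to A1C, the direct effect would tend to oppose the indirect one. In simulation, indirect and total effects were both significant in only about 1% (PHQ-9) and 5% (DFC) of such trials. This stands as a mitigation. But the plan does not require a significant total effect, and where treatment does lower A1C by another route the problem remains in full.

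**The reverse path is assumed.** This stands. The pilot correlations have no direction, and an example stressor does not show that A1C raises PHQ-9. The rates are conditional and mark the extreme at which the whole correlation is reverse.

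**Conflict is not a planned mediator.** This stands too. Sections 2.0 and 10.0 name depressive symptoms and parental involvement; conflict enters the mediation plan only through the power text. No correlation is given for parental involvement, so no rate can be computed for it.

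**Stronger readings that a reader might infer.** One is that the test would usually declare false mediation through PHQ-9. If same-visit A1C is the driver, a rate of about 65% needs a same-visit correlation of 0.20/0.60 = 0.33; the matching conflict value is 0.51/0.60 = 0.85, which is implausible. The stable-level model also gives about 62%, but the documents establish neither reading. Another is that adding 3-month A1C cures the problem and could decide the claim. It restores roughly 5% only if the measured 3-month value is the driver, and it conditions on a post-randomization value that may carry part of a real mediated effect.

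**Conclusion.** The concern holds as a gap in specification with a potentially large effect on the mechanism claim. With no mediator effect on A1C, and the pilot correlations taken as same-visit and wholly reverse, the planned test finds an indirect effect in about 28% of trials for PHQ-9 and 95% for conflict, and in about 12% if the correlation is only 0.10. The calculation rests on the protocol's N, A1C correlation and treatment-mediator correlations; the reverse path and its strength are assumptions. The documents do not support saying that the trial will report false mediation, only that the plan as written could not tell the two directions apart.

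**What to change.** In the mediation text of Section 10.0:

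1. Include the baseline mediator and baseline A1C in every A1C mediation model, at 6 and 12 months.
2. Pre-specify a companion sensitivity model that also includes 3-month A1C, and report it beside the main model. If the indirect effect does not persist there, describe the result as an association that may run from A1C to the mother, or may reflect an effect already present by month 3. Do not make the mediation claim depend on this model alone.
3. Extend the bidirectional analyses to include A1C.
4. Add a sensitivity analysis for unmeasured mediator-outcome confounding, because a stable A1C level as the driver is only partly removed by full adjustment.

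The cost is SAP wording, one extra model per mediator and A1C time point, and the added sensitivity analyses, all on measurements already planned. The companion model removes benefit already in A1C at month 3, with the power loss shown in Step 6. It can use only subjects with a 3-month A1C, which the analysis rule in Section 10.0 (baseline plus 6 or 12 months) does not guarantee, so its N may fall below 130.
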